2.5. Definitions for primary endpoint

2.5.1. Determination of Treatment Success/Failure

Treatment success is defined as controlled ocular inflammation (see Table 2) in both eyes with 7.5 mg/day of prednisone, no periocular or intravitreal corticosteroid injections after the first 90 days of follow up, and ≤ 2 drops/day of topical 1% prednisolone acetate at the 6 month visit without treatment failure any point due to safety, tolerability or futility. Patients can stop medication at any time, but that in and of itself does not count as a treatment failure.

Table 2: Criteria for controlled inflammation

Parameter	Definition of control
Anterior chamber cells*	$\leq 0.5+$
Vitreous haze**	$\leq 0.5+$
Choroid & retina***	No active inflammation or retinal vasculitis posterior to the equator

*SUN criteria³⁰; ** NEI vitreous haze grading scale³¹ *** Cystoid macular edema is not sufficient to be called active inflammation

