2.5.2. Treatment failure

- Failure due to efficacy:** Patients can be declared a treatment failure due to futility and be declared a treatment failure and enter Phase II **at any time during follow-up** if the following occurs: The treating physician determines that it is futile to continue the current study medication due to persistent, uncontrolled inflammation that appears to be non-responsive to treatment. This option of declaring futility should only be declared if treatment with study medication seems completely unlikely to be able to control inflammation. Since the medications take up to a few months to fully take effect, increase in inflammation early on in the trial is not an indication of treatment failure. Corticosteroids may be increased in the case of increased inflammation.

Efficacy will be judged at the primary endpoint of 6 months. Specifically, at 6 months, if there is a lack of efficacy, patients will be declared a treatment failure and enter Phase II if the following occurs: The patient does not have controlled inflammation (see Table 2) with a prednisone dose of 7.5 mg/day and less than or equal to 2 prednisolone acetate 1% drops per day by 6 months.

- Failure due to intolerance:** Patients who experience severe symptoms thought to be related to the drug should try a dose reduction if they are willing. If this is not successful and the patient is unable to continue their

medication due to symptoms and is also not willing to continue, treatment failure can be declared. Please refer to Table 5 for dose reduction guidelines. Trial of a dose reduction is strongly encouraged, however it **is not required** for a patient to be determined a treatment failure due to intolerability.

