For all patients, oral prednisone will be tapered gradually according to Standardization of Uveitis Nomenclature (SUN) guidelines (see Table 6). As it takes 6-8 weeks for the study medications to take full effect, it is expected that inflammation may become uncontrolled with a corticosteroid taper in some patients during the first 3 months of the study. This does not necessarily mean that the randomized treatment has failed, since more time may be needed to ensure the drug has reached its full effect. If the study ophthalmologist believes that continued treatment is futile prior to the primary endpoint, treatment failure may be declared and the patient should enter Phase II. If this occurs in Phase II, treatment failure will be declared and the patient should be treated according to best medical judgment. However, all patients should be followed up to their 6th month assessment in Phase II.

At any point in Phase I or Phase II, investigators have the option of reducing the prednisone dose, and following a faster taper, if the patient is experiencing severe side effects. However, it is strongly encouraged that investigators follow the corticosteroid tapering guidelines. If **absolutely medically necessary**, the investigator may digress from the protocol and reduce steroids below 7.5 mg/day in the first six months, but this is strongly discouraged.

The corticosteroid tapering schedule for Phase I (6-12 months) is optional, and physicians may taper patients as they deem medically acceptable. It is not mandatory for patients to reduce down to 0mg of prednisone by 12 months. In general, a rapid taper in Phase I months 6-12 is not recommended due to issues of adrenal insufficiency.

Table 6: Tapering schedule for oral prednisone: Phase I or if starting new medication in Phase II*

Dose (mg/day)	Duration (weeks)	Decrement (mg/day)
60	2 – 4 ¹	10
50	1	10
40	1	5
35	1	5
30	1	5
25	1	5
20	1	2.5
17.5	1	2.5
15	1	2.5
12.5	1	2.5
10	1	2.5
7.5	hold*	

NOTE: Begin patients at 1mg/kg or 60 mg/day, whichever is less. For Phase I hold patients at 7.5 mg/day, up to the end of 6 months.

*If starting Phase II and failed Phase I due to efficacy.

If uveitis does not improve at the end of the first 4 weeks, use best medical judgment regarding supplemental treatment (e.g. pulse dose treatment, corticosteroid injections, additional immunosuppressives).

Table 7: Optional tapering schedule Phase I (6-12 months)

Dose (mg/day)	Duration (weeks)	Decrement (mg/day)
7.5	1*	2.5

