< 7.5 & ≥ 5	2 – 4	1 - 2.5
< 5 & ≥ 2.5	2 - 4	1.5 - 2.5
< 2.5 & ≥ 1	2 – 4	1
0		

NOTE: When beginning Phase I (6-12 months), hold patient at 7.5 mg/day, for at least one week.

Directions for Rescue Taper

Reactivations can be mild or severe. Mild reactivations are considered an increase in inflammation up to the 1+ level in anterior chamber cell or vitreous haze. Severe reactivations are considered an increase in inflammation up to the 2+ level or higher in anterior chamber cell or vitreous haze. Retinal/choroidal lesions may be considered mild or severe at the discretion of the study physician.

If uveitis reactivates:

- Increase oral prednisone up to a dose of 1 mg/kg for severe reactivations, or for mild reactivations, up to double the dose at which the flare occurred, until uveitis is controlled. Then re-taper according to the guidelines.

Uveitis is considered non-responsive if inflammation does not increase but does not further improve after the first 4 weeks of treatment on 1mg/kg oral prednisone.

If uveitis is non-responsive:

- Hold the current dose of prednisone for an additional week. If still no improvement, treatment failure due to futility may be declared, and patients may proceed to Phase II. Alternatively, other therapies may be added, but these should be noted as a protocol deviation.
- If treatment failure is declared due to futility in Phase I, before the primary endpoint of 6 months, patients may switch to Phase II. Patients who refuse to switch to Phase II should be encouraged to return for a 6-month visit. Patients who switch to Phase II will already be followed.
- If treatment failure is declared due to futility in Phase II, before the primary endpoint of 6 months, patients will be treated according to best medical judgment. If treatment failure is declared prior to 6 months, Phase I and Phase II, every attempt must be made to bring patients back for their 6 month assessment.

After suppression of uveitis is once again achieved (either in the case of reactivation or non-response) follow the taper guidelines for Phase I. Patients who have failed the treatment to which they are randomized will then switch treatments, begin Phase II, and follow the same taper guidelines as Phase I (0-6 months). If patients flare during Phase II, they can follow directions for the rescue taper listed above. Patients who fail the second treatment at the 6 month endpoint will be treated as per the investigators discretion.

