3.2.4. Periocular and Intravitreal Injections

The use of periocular and intravitreal injections during the trial is strongly discouraged, as it hinders the ability to assess the study drugs' effectiveness for controlling inflammation. One injection, either periocular triamcinolone 40mg or intravitreal triamcinolone 4mg, may be administered to treat persistent macular edema during the first 90 days of follow-up if the investigator thinks this is medically necessary. One injection for persistent macular edema is permitted in the first 90 days of follow-up of Phase I, and similarly, one injection treating persistent macular edema is permitted in the first 90 days of follow-up of Phase II. If an injection is given at any time solely for the purpose of treating inflammation, a Protocol Deviation Form should be completed and sent to the Medical Monitor (██████████), Principal Investigator (██████████), and Coordinating Center Manager (██████████). If an injection is given for any reason after the first 90 days of follow-up of either Phase I or Phase II, a Protocol Deviation Form should be completed and sent to the Medical Monitor, Principal Investigator, and

Coordinating Center Manager.

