3.2.5 Other adjunctive treatments/procedures

The protocol dictates use of oral prednisone, corticosteroid drops and study medication (methotrexate or mycophenolate). The investigator may use other topical adjunctive medications such as IOP lowering medications and cycloplegic agents. These should be recorded on the Treatment Assessment form at each visit. The protocol does not allow for intravenous therapy, additional immunosuppressives or surgery during the study period. If such therapies are deemed necessary, the Protocol Deviation form should be completed and sent to the Medical Monitor, Principal Investigator, and Coordinating Center Manager.

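### The primary endpoint bars late steroid injections but sets no rule for added systemic immunosuppressives or pulse therapy, so a patient controlled by a non-study drug can count as a study-drug success

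*Combined protocol and SAP*

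**What the plan says.** **Primary definition.** Protocol 2.5.1 requires Table 2 control in both eyes, prednisone at 7.5 mg/day, at most two drops a day of topical steroid, "no periocular or intravitreal corticosteroid injections after the first 90 days of follow up", and reaching month 6 "without treatment failure any point due to safety, tolerability or futility". It adds: "Patients can stop medication at any time, but that in and of itself does not count as a treatment failure". The month-6 efficacy failure rule in 2.5.2 looks only at inflammation, prednisone and drops: "The patient does not have controlled inflammation (see Table 2) with a prednisone dose of 7.5 mg/day and less than or equal to 2 prednisolone" (the quote breaks off within the limit on drops). Neither section mentions other immunosuppressives, biologics, or intravenous or pulse steroid.

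**Handling of non-response.** Three places in the protocol bear on it:
- The note under Table 6 (3.2.1), for uveitis not improved after four weeks: "use best medical judgment regarding supplemental treatment (e.g. pulse dose treatment, corticosteroid injections, additional immunosuppressives". It does not mention a deviation.
- The rescue directions (3.2.1), for a non-responsive patient after one further week: futility may be declared, or, "Alternatively, other therapies may be added, but these should be noted as a protocol deviation".
- Section 3.2.5: "The protocol does not allow for intravenous therapy, additional immunosuppressives or surgery during the study period". If such therapy is judged necessary anyway, a deviation form is filed.

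**SAP.** Section 2.3.1 takes success from protocol 2.5.1. Section 3.2.2 sets the outcome to 0 for discontinuation through intolerance or adverse events, not for added therapy. Section 3.5.1 deals with injections only, as a sensitivity analysis. The alternative success definitions (3.2.2, item 11) concern unassessable fields and vitreous cells. The primary population is all randomized patients (4.1), analysed as complete cases (3.5). The major-deviation list (4.2) names injections but not added systemic drugs, although the list is open-ended.

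**The concern.** The same non-responsive patient can be scored in opposite ways depending on a discretionary choice. A futility declaration gives a failure. Added therapy gives a deviation note and leaves success open. Section 2.5.2 reserves futility for patients in whom control looks completely unlikely, so it cannot be assumed that most such patients will be declared failures.

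The plan's own reasoning argues against crediting the study drug in this situation. Protocol 3.2.4 discourages injections because they obscure the effect of the study drugs, and permits only a narrow exception: "One injection, either periocular triamcinolone 40mg or intravitreal triamcinolone 4mg, may be administered to treat persistent macular edema", within the first 90 days. SAP 3.5.1 says that the study drug cannot truly be assessed after a late injection. The same reasoning applies to a systemic agent that may still be running at month 6, yet no rule covers it.

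What is at stake is the primary comparison and the non-inferiority analysis planned if that comparison shows no difference (SAP 3.2.2, item 16).

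**Working it through.** **1. Can such a patient meet every criterion?** Under the rescue directions, non-response is judged after 4 weeks plus 1 held week, so at week 5. Table 6 has ten one-week steps from 50 down to 10 mg. If control is prompt, 7.5 mg/day is reached at about 5 + 10 = 15 weeks, some 11 weeks before month 6 (26 weeks). The rescue directions send a patient whose non-response has been suppressed back to this taper. With no futility declared and no injection after day 90, every condition in 2.5.1 is met. The patient attends month 6 and so enters the complete-case analysis. The month-6 dose condition does catch an oral steroid pulse still running at the visit. The gap is therefore widest for added immunosuppressives and for intravenous or earlier pulses.

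**2. The plan's own figure.** SAP 3.4.1 uses 40% versus 60%, two-sided 0.05, 80% power and 10% loss. Equation (5) gives 2N = 4 × (1.960 + 0.842)² × 0.25 / 0.04 = 196.2, and 196.2 × 1.1 = 215.8, the stated 216. With 108 per arm, 108 × 0.9 ≈ 97 are evaluable. Power with unpooled variance is Φ(0.20 / √[(0.24 + 0.24)/97] − 1.96) = 81%. A pooled null variance gives 80%. The sample-size arithmetic is sound.

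**3. Effect of the scoring gap.** Let u be the share of patients who would otherwise fail and are rescued, and c the share of those controlled at month 6. Both are assumptions, taken as equal in the two arms. Then:
- methotrexate rate = 0.40 + 0.60·u·c
- mycophenolate rate = 0.60 + 0.40·u·c
- difference = 0.20 × (1 − u·c)

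| u | c | Methotrexate | Mycophenolate | Difference (points) | Power, 97 per arm | Extra successes (methotrexate / mycophenolate) |
|---|---|---|---|---|---|---|
| 0 | – | 40.0% | 60.0% | 20.0 | 81% | 0 / 0 |
| 5% | 50% | 41.5% | 61.0% | 19.5 | 79% | 1.5 / 1.0 |
| 10% | 70% | 44.2% | 62.8% | 18.6 | 75% | 4.1 / 2.7 |
| 20% | 70% | 48.4% | 65.6% | 17.2 | 69% | 8.1 / 5.4 |

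**4. How far the direction depends on equal rescue.** If the converted shares differ, the difference in points is 20 − 60·f(methotrexate) + 40·f(mycophenolate), where f = u·c. It shrinks as long as f(mycophenolate) is below 60/40 = 1.5 times f(methotrexate). Above that ratio it would widen.

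**5. Fallback non-inferiority.** Take true rates of 50% versus 60%, exactly at the 10-point margin, and read the test as the lower 95% limit of methotrexate minus mycophenolate lying above −10 points. With f = 0.10 in both arms the rates are 55% and 64%, and the standard error is √[(0.55×0.45 + 0.64×0.36)/97] = 0.0702. The chance of declaring non-inferiority is Φ((−0.09 + 0.10)/0.0702 − 1.96) = 3.5%, against 2.5% with f = 0. At f = 0.20 it is 4.8%.

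**The case against.** Several objections have force.

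- **A reader might infer that the protocol both permits and forbids added therapy.** That goes too far for the rescue directions and 3.2.5, since both treat it as a deviation to be documented. The sharper conflict is with the note under Table 6, which leaves it to medical judgment without mentioning a deviation.
- **A reader might infer that an injection at month 2 or 3 would bar success while a systemic drug at that time would not.** It would not, because 2.5.1 bars injections only after day 90. The contrast holds only from that point.
- **A reader might infer that every week-5 non-responder is a study-drug failure turned into a success.** The documents do not support that. Section 3.2.1 says the study drugs need 6–8 weeks for full effect, and the first two weeks are at the introductory dose. Some of these patients would have succeeded anyway. The calculation counts only those who would otherwise have failed. That the worse drug collects more false successes is an inference from equal rescue rates and is not shown in the documents.
- **Estimand.** In a comparative-effectiveness trial, scoring month-6 status whatever else was given can be defended. But the plan never states that strategy, and its endpoint already scores declared futility and late injections as non-success.
- **Safeguards.** Examining ophthalmologists are masked, so the choice of option should not follow knowledge of the arm. The open-ended deviation list may remove such patients from the per-protocol population. Neither changes the primary analysis.
- **Missing material.** The primary endpoint flowchart and the study forms are not in the available text. The visible flowchart footnotes contain no such rule, but an instruction elsewhere cannot be excluded.

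**Conclusion.** The gap is real and should be fixed. As written, a patient controlled at month 6 with the help of a non-study systemic drug given for uveitis meets every stated criterion for success on the randomized drug, and discretion decides whether that patient is a failure or a success.

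If rescue is similarly frequent among non-responders in both arms, the effect is toward no difference. The size is unknown. The low case is negligible (19.5 points, 79% power). The highest case tabulated costs 2.8 points and about 12 points of power. The effect on the non-inferiority error is small. These figures rest on the SAP's planning rates, 97 evaluable patients per arm and rescue shares that the documents do not supply. The documents therefore do not support a claim that the primary result will be materially biased. They do support the claim that the endpoint leaves an avoidable misattribution open.

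**What to change.** Before any unmasked analysis, state in protocol 2.5.1 and SAP 3.2.2 how these patients are scored. A patient is not a success if a non-study systemic immunosuppressive, biologic, or intravenous/pulse corticosteroid was given **to treat uveitis** before the month-6 assessment. For corticosteroid, use the day-90 point that already applies to injections. Apply the same rule in Phase II. The indication limit matters: without it, a drug given for non-ocular disease would turn a controlled eye into a failure.

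At minimum, make this a named sensitivity analysis beside SAP 3.5.1 and name such therapy in the SAP 4.2 deviation list.

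Separately, the Table 6 note, the rescue directions in 3.2.1 and section 3.2.5 must be reconciled on whether such therapy is permitted or is a deviation. No view is taken here on which clinical rule is right.

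The cost is about one sentence in each document. Section 3.2.5 already requires a Protocol Deviation form for these therapies, so no new form should be needed, but the form should be checked to confirm that it records drug, date and indication. The downside is that observed success rates may be slightly lower, and some patients who would have responded to the study drug alone will be counted as failures.

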3.2.2. Supplements

All patients will be given recommendations for supplemental treatment. This treatment is important for patients receiving oral corticosteroids, in order to minimize the incidence of osteoporosis. Recommendations will include:

- Calcium supplement, 500 mg 3 times daily (unless contraindicated)
- Vitamin D, 400-800 IU daily.

3.2.3. Topical corticosteroid

In addition to oral prednisone, patients may enter the study on varying doses of topical corticosteroid drops. Topical corticosteroids should be tapered according to the suggested guidelines (Table 8). Various types of topical corticosteroids are acceptable. The chronic use of two times a day prednisolone acetate 1% was considered to be medically acceptable in a survey we conducted of the American Uveitis Society members. Thus, a dose of ≤ 2 drops a day prednisolone acetate 1% or equivalent corticosteroid will be considered sufficient in order to declare treatment success. If possible, the goal will be to completely taper off topical corticosteroids. In order to determine treatment success or failure, the equivalent amount of prednisolone acetate 1% would have to be determined, and if greater than 2 times a day treatment failure will be declared.

Table 8: Suggested tapering schedule for topical corticosteroid drops

Dose	Duration (weeks)
1 drop, 8-10 times a day	1-2
1 drop, 6 times a day	1
1 drop, 4 times a day	1
1 drop, 3 times a day	1
1 drop, 2 times a day	1
1 drop, 1 time a day	1
None	

3.2.4. Periocular and Intravitreal Injections

The use of periocular and intravitreal injections during the trial is strongly discouraged, as it hinders the ability to assess the study drugs' effectiveness for controlling inflammation. One injection, either periocular triamcinolone 40mg or intravitreal triamcinolone 4mg, may be administered to treat persistent macular edema during the first 90 days of follow-up if the investigator thinks this is medically necessary. One injection for persistent macular edema is permitted in the first 90 days of follow-up of Phase I, and similarly, one injection treating persistent macular edema is permitted in the first 90 days of follow-up of Phase II. If an injection is given at any time solely for the purpose of treating inflammation, a Protocol Deviation Form should be completed and sent to the Medical Monitor (██████████), Principal Investigator (██████████), and Coordinating Center Manager (██████████). If an injection is given for any reason after the first 90 days of follow-up of either Phase I or Phase II, a Protocol Deviation Form should be completed and sent to the Medical Monitor, Principal Investigator, and

Coordinating Center Manager.

3.2.5 Other adjunctive treatments/procedures

The protocol dictates use of oral prednisone, corticosteroid drops and study medication (methotrexate or mycophenolate). The investigator may use other topical adjunctive medications such as IOP lowering medications and cycloplegic agents. These should be recorded on the Treatment Assessment form at each visit. The protocol does not allow for intravenous therapy, additional immunosuppressives or surgery during the study period. If such therapies are deemed necessary, the Protocol Deviation form should be completed and sent to the Medical Monitor, Principal Investigator, and Coordinating Center Manager.

3.3. Study procedures

Enrollment/Baseline visit

Study coordinators should adhere to the following protocol for study procedures taking place at the enrollment visit.

- The patient's eligibility for participating in the study will be determined by the study ophthalmologist, aided by the study coordinator.
- If eligible, the patient will review the consent form with the study coordinator and the study physician, and give their consent.
- After consent, the study coordinator will assign the patient a unique Patient ID (derived from the list provided to study coordinator by the principal statistician).
- The study coordinator will then contact the designated person on site, holding the randomization list, to obtain the patient's drug assignment. This will be done away from sight of the study physician.
- The study coordinator will then label the medication with the assigned Patient ID. They should also place the appropriate number for the bottles (i.e. if it is the first bottle dispensed, it should have the #1 on the bottle).

Study visits

Study coordinators should adhere to the following protocol for study procedures taking place, after the patient is consented, enrolled and randomized. All study procedures should follow the schedule listed below:

- The patient comes for a study visit and meets with the study coordinator before their study doctor.
- The patient's medication bottle and folic acid bottle (*if applicable*) is immediately placed in a secure, opaque bag and left at the study coordinators desk for the remainder of the visit. Patient medication calendars should also be placed in the opaque bag.
- The study coordinator will check-in with the patient and complete the following in any order:
 - Review of patient medication diaries
 - Review of adverse events since last visit*
 - Dispense new medication bottle (*if applicable*)
 - Completion of SF-36 questionnaire (All patients) (*if applicable*)

- Completion of NEI-VFQ-25 (all patients) and IND-VFQ (Indian patients only)
- Remind the patient that they should not speak to their study doctor about their dosing schedule, or the name of the medication that they are currently taking.

*If the patient is experiencing intolerable side effects, the study coordinator and patient will speak to the doctor about the possibility of a dose reduction, without revealing the name of the medication or the dosing instructions. The study doctor will then decide if the dose reduction should be done and inform the study coordinator and patient. The study coordinator will then provide the patient with new dosing instructions, away from sight of study physician. A dose reduction is not mandatory but is encouraged in the setting of intolerability.

- The patient will then complete the study assessments, in the following order:
 - Visual Acuity Assessment
 - Slit lamp front of the eye exam and intra-ocular pressure
- The patient's eyes will then be dilated and the following assessments will be completed, in any order**:
 - Posterior segment exam
 - OCT imaging
 - Fundus photography
 - Fluorescein angiogram (not a study assessment, but if performed results should be recorded)
 - Laboratory measurements
- After completion of the study visit, the patient will meet with the coordinator, review scheduling for the next study visit, and retrieve their medication.

**It is essential that visual acuity measurements, front of the eye exams and intra-ocular pressure are completed *before* dilation of the eyes.

Data handling and data entry

After completion of each study visit, study coordinators at all sites will scan data collection forms and send them electronically in PDF format to the study email address ([REDACTED]). Hard copies of the forms should be kept in a secure location at each site. Study staff at [REDACTED] will perform double data entry of the PDF forms into a web-based REDCap database from which data can be electronically extracted for analysis. See section 7 for further details on the data entry process.

4. Study visits

